# 2.3 Objectives

The aim of this research is to ascertain the feasibility of performing a RCT comparing patient-reported functional outcomes and cost effectiveness of THA using either a fully cemented or a hybrid total hip implant.

#### Workstream 1:

#### **Primary**

To ascertain the feasibility of performing a comparative trial of hybrid or cemented implants for total hip replacement.

#### Secondary

#### To Assess:

- 1. Recruitment to a trial of this nature
- 2. Capture rate for postal/telephone follow-up
- 3. Rate of trial withdrawal
- 4. PROMS data statistics to determine the power required for the full study
- 5. Intra-operative and post-operative safety
- 6. To identify the incidence of treatment cross over during surgery
- 7. To determine the feasibility of conducting a within-trial cost-utility analysis

#### Workstream 2:

- 1. To understand patient experiences of the trial and their reasons for taking part or declining to participate
- 2. To understand surgeons' perceptions of the trial and equipoise, to establish factors underlying their willingness or unwillingness to participate in a trial, and to understand any barriers to implementation in practice of trial findings.
- 3. To understand health professionals experiences of recruiting participants to the trial and data collection, to learn about their thoughts regarding patient perceptions of the study, and to identify any changes that could enhance recruitment and running of the larger study.

#### 2.4 Potential Risks and Benefits

#### 2.4.1 Potential Risks

The risks of total hip replacement are fully understood and discussed with patients prior to surgery as part of the consenting for surgery process. All patients within the trial and who take part in qualitative interviews would be undergoing total hip replacement surgery even if they were not entered into the trial. All patients will have been assessed as being suitable to receive either type of hip implant as part of the study eligibility criteria; therefore participation within the trial does not pose any additional risks to the patients above routine care and no steps to mitigate risks of the surgery are required.

**IRAS Ref: 271885** Page 28 of 89

In interviews, when discussing their experiences of surgery, the trial, and recovery, it is possible that patient participants could talk about issues they find upsetting such as worries about surgery or pain. Should any participant show signs of distress then the study distress policy will be followed.

There are no anticipated risks for surgeon or other health professional participants taking part in interviews.

#### 2.4.2 Known potential Benefits

The potential benefits of hip replacement surgery are well known. The purpose of the study is to try and identify any possible benefits of one type of implant over the alternative. Patient participants will be confirmed by an investigator as being suitable to receive either type of implant.

There are no specific benefits of taking part in the qualitative interviews, but people sometimes find it helpful to talk about their experiences with an interested individual.

**IRAS Ref: 271885** Page 29 of 89

## 3 SELECTION OF SITES/CLINICIANS

For the purposes of clarity, use of the words 'Site', 'Centre' and 'Hospital' are interchangeable references for the locations the participants will be recruited from and will differ depending on the context in which they are used.

For Workstream 1, each participating Site (and Investigator) has been identified on the basis of:

- Having at least one lead surgeon with a specific interest in, and responsibility for, managing patients who undergo total hip arthroplasty.
- Showing enthusiasm to participate in the trial
- Ensuring that sufficient time, staff (including research nurses) and adequate facilities are available for the trial
- Providing information to all supporting staff members involved with the trial or with elements of the patient's management
- Acknowledging and agreeing to conform to the administrative and ethical requirements and responsibilities of the trial, including voluntarily agreeing to follow the relevant aspects of the Good Clinical Practice (GCP) guidelines.

For Workstream 2, participating sites have either been involved in Workstream 1 or (for some surgeons who will be interviewed) are sites that the research team have identified as possible further sites for the full, definitive trial.

#### 3.1 Site/Clinician Inclusion Criteria

- a. Organisation Information Document
- b. Research Site Agreement
- c. Confirmation of capacity and capability from NHS Trust
- d. Receipt of evidence of the above by LCTC

## 3.2 Site/Clinician Exclusion Criteria

Those sites who do not fulfil the above inclusion criteria will not be permitted to participate in the trial.

**IRAS Ref: 271885** Page 30 of 89

## 4 TRIAL DESIGN

# 4.1 Overall Design

HipHOP is a randomised feasibility study in preparation for a phase III, two arm, blinded, multi-centre, pragmatic randomised controlled trial comparing fully cemented and hybrid total hip arthroplasty in patients undergoing total hip arthroplasty.

This feasibility study will have both quantitative and qualitative elements, referred to as Workstream 1 and Workstream 2 respectively.

The Workstream 1 population is patients undergoing a primary total hip arthroplasty. Patient participants will be recruited from three sites and randomised to the two arms of the trial to receive either a fully cemented hip implant, or a hybrid hip implant. A total of 40 patient participants will be randomised on a 1:1 ratio. Recruitment will take approximately 6 months. Patient participants will be blinded to the type of hip prosthesis received. All possible efforts will be made for the patient participants to remain blinded until their 3-6 month post-operative PROMS are completed to ensure the integrity of the outcomes reporting. Staff collecting outcome data will also be blinded where possible (see section 9).

There are no exclusions to the *size* of socket used in the procedure. Deviation from the socket *type* that is selected at random is allowed, but only if it is established during surgery that the randomised socket type is unsuitable.

Comparison of the types of implant will be made using data collected using Patient Reported Outcome Measures. A healthcare resource use survey will also be provided to patients to complete. Data from this survey will be used to determine if a cost analysis will be possible in a larger phase III study.

Participants would have reached the end of their study involvement once their 3-6 month post-operative visit has been completed.

The Workstream 2 population is patients who both accepted or declined participation in Workstream 1, consultant orthopaedic surgeons and other health professionals.

# 4.2 Endpoints

The intention is to investigate the rate of recruitment, plus compliance with study procedures and assessments, in patients undergoing a primary total hip arthroplasty. Additionally, patients will be interviewed to elicit their reasons for accepting or declining the invitation to participate and their experiences of trial procedures. Consultant surgeons will also be interviewed for their views on their willingness to enrol patients in a total hip arthroplasty trial and about any barriers there might be to changing their surgical practice following the results of a larger phase III trial. We will also interview health professionals who have been involved in the recruitment of patients, or who have collected patient self-reported data, for their experiences of trial procedures and patients' willingness to participate.

Primary and Secondary Endpoints, along with their measures, are described in detail in section 11.2.

**IRAS Ref: 271885** Page 31 of 89

# **WORKSTREAM 1**

(Referred to as 'Part 1' in participant documentation)

**IRAS Ref: 271885** Page 32 of 89

## 5 STUDY POPULATION

The population is patients undergoing a primary total hip arthroplasty.

# 5.1 Eligibility Criteria

The HipHOP trial aims to recruit 40 patient participants based on sample size calculations described in section 11.3. All patient participants must provide written, informed consent before any study procedures occur (see Section 6 for more information regarding the informed consent processes) and must meet all eligibility as described below.

#### **Inclusion Criteria**

Potential patient participants eligible for the trial must comply with all of the following at randomisation:

- 1. Age 18 years and above
- 2. Undergoing a primary total hip arthroplasty with either a fully cemented or hybrid implant
- 3. Able to give informed consent prior to randomisation
- 4. Able to communicate in both written and spoken English

#### **Exclusion Criteria**

Any patient participant meeting any of the criteria listed below prior to randomisation will be excluded from study participation:

- 1. Previous surgery to the hip joint.
- 2. All procedures with an indication other than osteoarthritis
- 3. Patient requiring complex total hip arthroplasty surgery, specifically augmentation of the acetabulum (e.g. structural bone graft or metal augment) and/or shortening/de-rotational osteotomy of the femur at the time of surgery.
- 4. Patients requiring bilateral simultaneous total hip arthroplasty
- 5. Vision impairment that precludes the completion of PROMS questionnaires.

# 5.2 Patient Participant Transfer and Withdrawal

In consenting to the trial, patient patients are consented to trial treatment, follow-up and data collection. If post-operative voluntary withdrawal occurs, the participant should be asked to allow continuation of scheduled evaluations, and be given appropriate care under medical supervision until the symptoms of any adverse event resolve or the subject's condition becomes stable.

Participants who lose capacity after providing consent and while still in follow-up will be withdrawn from the study. In these instances, data up to the point of withdrawal will still be used for analysis and the patient will not be replaced.

\_

<sup>2 All prostheses and bone cements that are used must be CE marked and used in accordance with their intended use. There is no limitation as to the manufacturer of prostheses used and surgeons will continue to use the implants that they are familiar with. Furthermore, surgeons will be free to use whichever head/socket material and diameter they feel appropriate. The surgical approach, anaesthetic type, rehabilitation after surgery and other concomitant factors will be as per the surgeons' normal care. These factors will be recorded.

**IRAS Ref: 271885** Page 33 of 89

## 5.2.1 Participant Transfers

Due to the low number of participating sites and their geographical difference, it is unlikely that participants relocating to another part of the country will be able to be followed-up at another hospital that is participating in HipHOP. However, every effort should be made for the participant to be followed-up at another participating site, and for this site to take over responsibility for the patient participant.

Should a transfer be possible, a copy of the participant CRFs should be provided to the new site. The patient participant will remain the responsibility of the original site until the PI at the new site has signed the Transfer CRF.

In the event of any transfer, the informed consent obtained by the original site remains valid; i.e. consent does not have to be re-obtained.

#### 5.2.2 Withdrawal from Trial Intervention

If a patient participant who has already given consent, or their surgeon, decides the operation cannot go ahead, consented participants will be withdrawn from the study.

Patient participants who withdraw from the study in this manner, and prior to undergoing their total hip arthroplasty surgery will be replaced.

Patient participants may be withdrawn from the study for any of the following reasons:

- a. Participant withdraws consent.
- b. Intercurrent illness preventing surgery.
- c. Pregnancy.
- d. Any other change in the patient participant's condition that justifies the prevention of surgery or follow-up in the clinician's opinion.

If a participant wishes to withdraw from post-op completion of PROMS, sites should explain the importance of remaining on trial follow-up, or failing this, of allowing data from the routine six-week follow-up visit to be used for trial purposes.

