# 6.3 Loss of Capacity after providing consent

Should a patient lose capacity during the study they will be withdrawn from any future participation. See section 5.2 for further details.

[figure not shown]
**IRAS Ref: 271885** Page 36 of 89

Decision Tree 1 – Patient identified at a surgical clinic appointment

**IRAS Ref: 271885** Page 37 of 89

Decision Tree 2 - Patient identified from a THA operation waiting list

**IRAS Ref: 271885** Page 38 of 89

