#### 9 BLINDING

To prevent bias in the completion of their answers to PROMS questionnaires, it is key that for the duration of their time on the study, i.e. until the 3-6 month post-operative PROMS questionnaires have been completed, a patient participant remains blinded to the type of implant they have received.

It is acknowledged that it is impossible to blind the surgeon, operation team and other healthcare professionals to the type of implant the patient participant received. Members of the research team being aware of the implant type will have no bearing on the outcomes of the study, however every effort must be made to ensure that patient participants remain blinded to the type of implant they received, at least until a patient has completed their 3-6 months post-operation PROMS questionnaires. These efforts must include, but are not limited to:

- Excluding members of the research team from correspondence that reveals the randomised allocation of the type of implant.
- Ensuring the patient is provided with and wears ear plugs during surgery.
   Alternatively, they can provide their own device and earphones to listen to music etc. instead (earphones do not have to be to any particular standard or specification, e.g. 'noise cancelling').
- Ensuring post-operative documentation that the patient or research team may have access to (e.g. discharge letter, physiotherapy referral) do not refer to the type of implant used.
- Marking/Annotating the operation notes to advise the reader to not disclose or allude to the type of implant used when in communication with the patient or research team.

If a patient participant does accidentally becomes unblinded to the type of implant they have received, the relevant CRF will need to be completed and returned to LCTC. Such occurrences will be recorded as protocol deviations but will not affect the patient continuing participation in the trial. Corrective and preventative actions must be undertaken locally to prevent similar events leading to unblinding to other patients.

If a member of the research team accidentally becomes unblinded to the type of implant patient receives, it does not have to be reported to LCTC. Corrective and preventative actions must however be undertaken locally to prevent the patient becoming aware, e.g. remove/reduce interaction between the member of the research team and the patient participant if possible.

**IRAS Ref: 271885** Page 47 of 89

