## 11.5 Analysis Plan

Feasibility and overall recruitment rate will be assessed at the opened sites by calculating the total number of patient participants randomised per month and the ratio of successful recruitment to eligible patients approached. Furthermore, observed recruitment rates, by site and overall, will be summarised along with a 95% confidence interval.

**IRAS Ref: 271885** Page 51 of 89

Much of the analysis will be performed using summary statistics and graphics. No formal assessments of efficacy, cost or safety across treatment arms will be made. All presentations of the data will take the form of summary analysis and graphical representations. Continuous data shall be presented using measure of median (interquartile ranges), whereas categorical data shall be presented in terms of frequencies of counts and associated percentages.

Primary and secondary outcomes will be compared between the two arms using a chisquared or Fisher's exact test.

All analyses shall be carried out on an intention to treat basis, retaining all patient participants in their initially randomised groups irrespective of any protocol deviations. The exception to this is the analysis of safety data which shall be analysed on the safety set which is defined by the type of arthroplasty that patients receive.

Feasibility of the study will be measured on the ability of the study to meet the recruitment targets and Stop/go criteria are defined on this basis.

Following 6 months of active recruitment, a target of 40 patient participants is set. If recruitment is  $\geq$  80% of this target ( $\geq$ 32 patients) a future full study can be considered feasible. If the observed recruitment rate is between 50% and 80% of the target (20-31 patients) then a future full study could potentially go ahead only if satisfactory measures can be taken to improve recruitment. Such measures must be realistic and have support of the study sponsor. If recruitment is less than 50% of the anticipated rate ( $\leq$ 19 patients) than the study won't be considered feasible to evolve into a full one in the future.

In addition, in order for the study to be considered feasible, it should not demonstrate any serious issues related to randomisation process, patient participant retention and/or protocol deviations.

Statistical analyses will be performed using a suitable recognised statistical software such as Stata v15 or above, R v3.3.0 or above and SAS v9.3 or above.

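### Section 5.2.2(d) lets an unblinded clinician end a patient's follow-up, which permits avoidable, outcome-related loss of the PROM data meant to size the full trial

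*Protocol*

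**What the plan says.** Protocol section 5.2.2 is headed as withdrawal from the trial intervention, but its list has a wider reach: "Patient participants may be withdrawn from the study for any of the following reasons". Item (d) of that list reads "Any other change in the patient participant's condition that justifies the prevention of surgery or follow-up in the clinician's opinion". It gives no criteria, is not limited to the period before surgery, and names follow-up separately from surgery.

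Section 9 states that "it is impossible to blind the surgeon, operation team and other healthcare professionals" to the implant type.

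For voluntary withdrawal after the operation, section 5.2 says "the participant should be asked to allow continuation of scheduled evaluations". Section 5.2.2 adds that sites should explain the importance of staying on follow-up to a participant who wishes to stop the post-operative questionnaires. Both provisions concern a decision by the patient. Neither covers a withdrawal initiated by the clinician.

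Sections 7.5 and 7.6 show what remains after surgery: a routine outpatient visit at 6 weeks with questionnaires, then postal questionnaires at 3-6 months with questions about return to theatre and unplanned contact. Section 2.2 says the full trial's sample size needs the standard deviation and the loss to follow-up of these scores. Section 11.3 plans to report the variance of PROM change, with its standard error and 95% confidence interval, from one longitudinal model of all data.

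**The concern.** Once the operation is done, the intervention is complete and withdrawal can only stop data collection. A worse condition after surgery is what the Oxford Hip Score and the other questionnaires exist to record, so by itself it is a poor reason to stop collecting them. Item (d) nevertheless allows that, on the opinion of someone who knows the implant, and without the step that would keep a voluntary withdrawer in follow-up.

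Two outputs of the feasibility study are exposed. If the patients removed are those with the lowest scores, the observed spread of PROM change is too narrow and a full trial planned on it is too small. The withdrawal rate would also mix losses chosen by patients with losses imposed by clinicians, although the full trial could avoid the second kind by wording alone.

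**Working it through.** **Figures in the protocol.** It states no SD, no expected withdrawal rate and no power calculation, so it has no figure of its own to reproduce on this point. Its one derived design figure, 40/(3 × 6) = 2.22 patients per site per month (section 11.3), is correct and plays no part here. Everything below except N = 40 and 1:1 allocation is an assumption.

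**Withdrawal rate.** The denominator is all randomised patients (section 11.2.2). One clinician-imposed withdrawal adds 1/40 = 2.5 percentage points overall, or 1/20 = 5 points within an arm. With four, retention is 36/40 = 90% (exact 95% CI 76% to 97%).

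**Variance, extreme case.** Outcomes were simulated as normal with n = 40 and 100,000 samples. The lowest k values were removed and the mean sample variance compared with that of all 40. For the consequence, assume a full trial planned at 90% power, two-sided 5%, for a standardised effect of 0.3. Then n per arm = 2(1.96 + 1.2816)² × v / 0.3² ≈ 233.5v, where v is the variance ratio. The true power of that n is taken at the true variance.

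| Worst patients lost | Retention | Variance ratio v | SD ratio | n per arm planned | True power |
|---|---|---|---|---|---|
| 0 | 100% | 1.00 | 1.00 | 234 | 90% |
| 1 | 97.5% | 0.89 | 0.95 | 209 | 87% |
| 2 | 95% | 0.83 | 0.91 | 193 | 84% |
| 3 | 92.5% | 0.77 | 0.88 | 180 | 81% |
| 4 | 90% | 0.73 | 0.85 | 170 | 79% |

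The variance falls by about 11% to 27%.

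**Variance, partial selection.** Suppose each patient in the worst fifth is withdrawn with probability p. For a standard normal cut at −0.8416 (density 0.2800), the worst fifth contributes 0.2 + 0.8416 × 0.2800 = 0.4356 to the second moment and −0.2800 to the first. The variance among those kept is therefore

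(1 − 0.4356p)/(1 − 0.2p) − [0.2800p/(1 − 0.2p)]².

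At p = 0.5 this is 0.7822/0.90 − (0.14/0.90)² = 0.869 − 0.024 ≈ 0.84. Simulation gives 0.99, 0.97, 0.93 and 0.84 for p = 5%, 10%, 25% and 50%, a fall of about 1% to 16%.

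**Sampling error for comparison.** The 95% CI for a variance on 39 degrees of freedom is 39/χ²(0.975) to 39/χ²(0.025), which is 0.67 to 1.65 times the estimate.

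All the reductions above lie inside that interval. The two errors differ in kind, however. The planned confidence interval shows the sampling error, whereas selective loss shifts the estimate one way and the interval does not show it.

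**The case against.** The strongest reply is that item (d) is a permissive catch-all in a section mainly about operations that cannot go ahead, and that nothing tells clinicians to remove patients with poor hip results. After surgery the rest of the protocol pushes the other way. Voluntary withdrawers are asked to continue, two calls and a letter precede loss to follow-up (section 7.7), visits outside the window do not end participation (sections 7.5 and 7.6), and re-interventions are recorded (section 7.9). This stands as a reason to expect few such withdrawals. It also shows that item (d) is out of line with the protocol's own policy.

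Several stronger readings are tempting, and the documents do not support them.

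- **Conflict with intention to treat.** A reader might infer one. Section 11.5 speaks of "retaining all patient participants in their initially randomised groups irrespective of any protocol deviations". Withdrawal leaves a patient in the randomised group with later data missing, so the grouping is not contradicted.
- **Biased retention.** Section 11.2.2 measures withdrawal against all randomised patients and shows it by reason and stage for both arms. Clinician-imposed losses are counted and can be separated. The rule changes what the rate means; it does not hide anyone.
- **Loss of capacity as the same defect.** Sections 5.2 and 6.3 withdraw such patients ("Should a patient lose capacity during the study they will be withdrawn from any future participation"). That is a consent safeguard and an ethics choice. It does not depend on opinion of the hip result, and the questionnaires are self-completed.
- **Bias between the arms.** Unblinded discretion could differ by arm, but nothing in the protocol shows that it would. Section 11.5 plans no formal efficacy assessment across arms, although it also mentions chi-squared or Fisher's exact tests.
- **A severely undersized full trial.** Extreme assumed score levels could give a larger shortfall, but the protocol supplies no scores, and section 11.3 concerns the variance of change from a longitudinal model. Baseline and any 6-week data in that model can reduce the bias as far as they explain the withdrawal.

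**Conclusion.** The concern holds as a minor design weakness. As worded, item (d) permits study withdrawal from follow-up on an unblinded clinician's opinion, without criteria and without the request for continued evaluations that voluntary withdrawers receive. The data at risk are those the feasibility study is meant to supply.

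The size is modest and conditional. A variance 11% to 27% too low requires that the very worst 1 to 4 of 40 patients are the ones removed. With partial selection it is 1% to 16%. Both rest on normal scores, on withdrawal that depends on outcome beyond what earlier data explain, and on an analysis that does not recover the loss. The fall in power to between 87% and 79% also rests on the assumed effect of 0.3 and planned power of 90%. No bias has been demonstrated, and sampling error at n = 40 is wider than any of these effects.

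**What to change.** - In section 5.2.2(d), delete *or follow-up*, so that the item concerns only a change that prevents surgery.
- In section 5.2.2, separate not receiving the intervention from ending data collection. The heading now names the first while the list brings about the second.
- In section 5.2, extend the request for continued evaluations from voluntary withdrawal to every post-operative withdrawal other than loss of capacity. Leave the loss-of-capacity rule as it is.
- State that a patient too unwell to complete questionnaires at one time point is recorded as missing with a reason and approached again at the next.

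The cost is wording in sections 5.2 and 5.2.2 at the next amendment, which section 13.1 requires to be submitted and approved before use. No visits or questionnaires are added. The small downside is that clinicians lose discretion to end the questionnaires. The participant can still decline at any time.
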